5.2 Radiation therapy

5.2.1 Simulation: Will be performed prior to initiation of therapy with patients in the supine position and arms above the head. One Vac-Lock bag will be used for positioning and immobilization placed at the level of the pelvis. No oral or IV contrast is required. CT simulation from the cranial extent of L1 to the level of the lesser trochanter will be performed to ensure adequate coverage and dosimetric parameters.

5.2.2 Volumes: The gross tumor volume (GTV) should be contoured using all available imaging as well as information from physical examination and proctoscopy.

The clinical target volume (CTV) should include the GTV as well as elective lymph node regions (internal iliac, mesorectal, presacral). Since patients with low lying rectal tumors and T4 rectal tumors will not be included in this study, the external iliac and inguinal lymph nodes should not be included as they are not felt to be at a significant clinical risk of subclinical involvement. A planning target volume (PTV) should be created using a 0.5 cm uniform expansion from the CTV to account for daily set up variability provided daily kilovoltage (kV) imaging is used for image guidance. If daily kV imaging is not available, then larger PTV margins should be used based on the discretion of the treating physician. Normal structures to be contoured include small bowel (up to 1 cm superior to PTV), bladder, femoral heads, and pelvic bones (including the sacrum, ilium, ischium, and pubic bones as a surrogate for bone marrow).

5.2.3 Technique: To limit dose to bone marrow, LDFRT will be delivered using intensity modulated radiation therapy (IMRT). IMRT may be delivered using either static beams or volumetric-modulated arc therapy (VMAT). Since the total prescribed radiation dose used in this study is well below the established tolerance levels of all normal tissues that will be contoured, no specific normal dose constraints should be used. However, a priority should be made to limit the volume of the pelvic bones (as a surrogate for bone marrow) receiving the prescription dose.

5.2.4 Dose: 40 cGy fractions will be administered twice daily on Days 1 and 2 of each cycle of FOLFOX with each radiation fraction being delivered [a minimum of 4](#) hours apart. This will be repeated every 2 weeks for a total dose of 960 cGy.

5.2.5 Treatment Planning Objectives:

100% of the PTV should be covered by at least 95% of the prescription dose. 100% of the CTV should be covered by at least 95% of the prescription dose. No greater than 110% of the prescription dose should be delivered to no greater than 0.03 cc of the PTV.

6.0 RESTAGING

Restaging will take place 4 weeks (± 1 week) after completion of 6 cycles of FOLFOX and LDFRT. The patient will see the physician and have labs and imaging completed per Appendix I scheduling. Repeat imaging should include the same modality used at baseline. For example, if a baseline MRI was performed, a post-LDFRT-FOLFOX MRI should be repeated. If a baseline endorectal ultrasound (ERUS) was performed, a post-LDFRT-FOLFOX ERUS and CT scan should be repeated.

The decision to proceed to TME directly, or alternatively receive standard chemoradiation off protocol followed by TME, will be based on radiological and clinical tumor response.

Patients will proceed directly to TME unless any of the following occurs, at which time they will be discontinued from treatment on this study and be recommended to pursue appropriate treatment off-study.

- If there is any evidence of progressive disease (PD) by either imaging or clinical assessment.
- If a patient with radiologically measurable disease has an overall radiologic tumor response status of stable disease (SD).
- If a patient with disease that is not radiologically measurable has a clinical tumor response of 20% or less as determined by endoscopy.

6.1 Radiological tumor evaluation

Assessment will be according to the revised Response Evaluation Criteria in Solid Tumors (RECIST) guidelines, version 1.³⁹

6.1.1 Timing of restaging evaluation: Patients should undergo re-evaluation 4 weeks (\pm 1 week) after the completion of 6 cycles of FOLFOX and LDFRT.

6.1.2 Definitions of measurable and non-measurable disease

6.1.2.1 Measurable disease (standard definition per RECIST):

- A non-nodal lesion is considered measurable if its longest diameter can be accurately measured as at least 2.0 cm with chest x-ray, or as at least 1 cm with CT scan, CT component of a PET/CT or MRI.
- A superficial non-nodal lesion is measurable if its longest diameter is at least 1 cm in diameter as assessed using calipers or imaging.
- A malignant lymph node (LN) is considered measurable if its short axis is at least 1 cm when assessed by CT scan or pelvic MRI

6.1.2.2 Non-measurable disease (standard definition per RECIST):

- All other lesions or sites of disease are considered non-measurable disease, including pathological nodes (those with a short axis at least 1 cm to less than 1.5 cm. Bone lesions, leptomeningeal disease, ascites, pleural/pericardial effusions, lymphangitis cutis/pulmonis, inflammatory breast disease, and abdominal masses (not followed by CT or MRI) or considered non-measurable as well.

6.1.3 Guidelines for evaluation of measurable disease

6.1.3.1 Measurement methods

- All measurements should be recorded in metric notation (i.e. decimal fractions of centimeters) using a ruler or calipers.
- The same technique and method of assessment must be used at baseline and during follow-up.

6.1.3.2 Acceptable modalities for measurable disease

- Conventional CT and MRI: This guideline has defined measurability of lesions on CT scan based on the assumption that CT slice thickness is 5 mm or less. If CT scans have slice thickness greater than 5 mm, the minimum size for a measurable lesion should be twice the slice thickness.
- For this study, when an MRI is performed, the technical specifications of the scanning sequences used should be optimized for the evaluation of the type and site of disease. The lesions should be measured on the same pulse sequence. Ideally, the same type of scanner should be used and the image acquisition protocol should be followed as closely as possible to prior scans. Body scans should be performed with breath-hold scanning techniques, if possible.
- PET-CT: The CT portion of the PET-CT can be used for RECIST measurements and can be used interchangeably with conventional CT in accurately measuring cancer lesions over time.
- Evaluation of disease by MRI is preferred. However, for patients who are not able to undergo an MRI or for clinicians who prefer it, an ERUS is acceptable. If ERUS is performed as an alternative to MRI at baseline, then an ERUS must also be performed at the time of restaging.
- In cases where ERUS is the modality selected to evaluate the primary rectal tumor, an accompanying CT for complete pelvic disease staging will also be interpreted by the on-site radiologist.
- A standard CT of the abdomen and pelvis or chest, abdomen and pelvis with oral and intravenous contrast is required. In the event that radiologic studies yield inconsistent interpretation of T stage or N stage the modality that assigns the highest T stage or the highest N stage should be used for purposes of protocol eligibility.

6.1.4 Measurement of effect – imaging response to neoadjuvant LDFRT-FOLFOX

“Adapted RECIST” as defined in this protocol consists of the following:

6.1.4.1 Target Lesions & Target Lymph Nodes

- The Rectal Primary tumor is the primary target lesion. In addition, associated pelvic lymph nodes should be recorded and measured at baseline.
- The primary rectal lesion is measured and followed as a bi-dimensional product to avoid measurements that include the GI tract lumen whether collapsed or filled with air, feces or contrast material that does not represent tumor tissue. The Bi-Dimensional Product (BDP) is the product of the longest diameter for the rectal primary tumor and the thickest wall. The BDP will be used as reference to further characterize

any objective tumor response in the measurable dimension of the disease.

- Post-Baseline Bi-Dimensional Product (PBDP): The product of the longest diameter of the rectal primary tumor multiplied by the thickest wall will be calculated and reported as the post-bi-dimensional product (PBDP). If the radiologist is able to provide an actual measure for the target even if it is below 0.5 cm. If the target is believed to be present and is faintly seen but too small to measure, a default value of 0.5 cm should be assigned. If it is the opinion of the radiologist that the rectal primary has likely disappeared, the measurement should be recorded as 0 cm.
- Given increased error in measuring smaller structures, and given differing qualities of MRI and their resolution, diminutive nodes are those measuring 0-0.4 cm. These will not be considered evaluable for change. Evaluable nodes are those 0.5 cm or greater in the mesorectal and superior hemorrhoidal location.
- To be labeled as a target lymph node: up to 4 nodes in the mesorectal, superior hemorrhoidal and internal iliac regions may be considered “target” lymph nodes if they measure 0.5 cm or greater in short axis.
- To categorize the primary tumor as consistent with clinical stage N2 disease, ≥ 4 lymph nodes must measure >1 cm in short axis.

6.1.4.2 Imaging Response Criteria

6.1.4.2.1 All target lesions and target lymph nodes followed by imaging and physical examination must be measured on reevaluation at evaluation times specified in Section 6.1. Specifically, a change in objective status to either a PR or CR cannot be made without re-measuring target lesions and target lymph nodes.

6.1.4.2.2 For purpose of restaging, a target lymph node must measure 0.5 cm or more in short axis.

- Target lymph nodes, which at baseline measure between 0.5 and 1 cm short axis inclusive, must increase 0.3 cm in size to be considered PD. Nodes between 1.1 and 2 cm short axis inclusive must increase in size 0.4 cm to be considered PD. Nodes 0.2 cm and greater in short axis must increase in size by 25%, (e.g., 0.2 cm to 2.5 cm, or 2.5 cm to 3.1 cm) to be considered PD.
- An internal target iliac lymph node (“obturator,” etc.), must be

1 cm in short axis diameter to be considered evaluable and will follow same rules as above for absolute increase in size.

- Complete LN response requires radiological disappearance of initially abnormal lymph nodes or maintenance of 1.9 cm or less size of LN from this baseline “normal” definition.

6.1.4.2.3 Evaluation of the Rectal Primary and Target Lymph Nodes.

1. Complete Response (CR)	All of the following must be true: a. Disappearance of the rectal primary. b. Each target lymph node must have decreased short axis to <0.5 cm. c. No new sites of disease.
2. Partial Response (PR):	At least a 20% decrease in PBDP (bi-dimensional product of primary rectal lesion) taking as reference the BDP. No new sites of disease. And no PD of any target lymph nodes.
3. Stable disease (SD)	Neither sufficient shrinkage to qualify for PR nor sufficient increase to qualify for PD.
4. Progression (PD)	At least one of the following must be true: At least one new malignant lesion, which also includes any LN that was normal at baseline (< 0.5 cm short axis) and increased to ≥ 0.5 cm short axis during follow-up. At least a 20% increase in PBDP (bi-dimensional product of rectal primary lesion).

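### The 25% nodal-progression tier in Section 6.1.4.2.2 is misprinted as starting at 0.2 cm instead of 2 cm; once corrected, one tie remains at exactly 2.0 cm

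*Combined protocol and SAP*

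**What the plan says.** Section 6.1.4.2.2 grades nodal progression in three tiers by baseline short axis. The first covers target nodes "which at baseline measure between 0.5 and 1 cm short axis inclusive, must increase 0.3 cm in size to be considered PD". The second reads "Nodes between 1.1 and 2 cm short axis inclusive must increase in size 0.4 cm to be considered PD". The third is relative, not absolute: "Nodes 0.2 cm and greater in short axis must increase in size by 25%, (e.g., 0.2 cm to 2.5 cm", followed by a second example of 2.5 cm growing to 3.1 cm.

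Two other provisions set the smallest node that can enter these tiers. Section 6.1.4.1 states that "diminutive nodes are those measuring 0-0.4 cm. These will not be considered evaluable for change". Section 6.1.4.2.2 itself opens with "For purpose of restaging, a target lymph node must measure 0.5 cm or more in short axis".

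The tiers feed the response table in Section 6.1.4.2.3, where partial response carries the condition "And no PD of any target lymph nodes". Response status in turn feeds Section 6.0: "Patients will proceed directly to TME unless any of the following occurs". The listed exceptions include progressive disease and, where disease is radiologically measurable, stable disease.

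**The concern.** A progression rule should assign each evaluable node to one tier with one cut-off. As printed, this one does not. The third tier starts at a size that the same section excludes from target status, and it sits on top of the two tiers before it. Its first worked example does not illustrate the percentage it is meant to illustrate.

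The rule is used for decisions. If the primary tumor has shrunk enough for partial response but a target node is called progressive, the patient is not a partial responder. With measurable disease, stable and progressive disease both lead off the direct path to total mesorectal excision (TME). The nodal cut-off can therefore decide whether a responding patient goes straight to surgery, where the primary endpoint, pathological complete response (pCR), is read.

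**Working it through.** **Inputs.** From 6.1.4.2.2: tier 1, baseline 0.5 to 1.0 cm, +0.3 cm; tier 2, baseline 1.1 to 2.0 cm inclusive, +0.4 cm; tier 3, start printed as 0.2 cm, +25%; examples 0.2 to 2.5 cm and 2.5 to 3.1 cm; target-node minimum 0.5 cm. From 6.1.4.1: nodes of 0 to 0.4 cm are not evaluable for change.

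**Step 1: the worked examples.** Percent increase = (follow-up / baseline − 1) × 100.

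- First example as printed: 2.5 / 0.2 − 1 = 11.5, or +1150%. The stated 25% is not reproduced.
- First example with 2 cm: 2.5 / 2.0 − 1 = 0.25, exactly +25%.
- Second example: 3.1 / 2.5 − 1 = +24%. An exact 25% is 2.5 × 1.25 = 3.125 cm, which rounds to 3.1 cm. I treat this as rounding, not as an error.

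**Step 2: can a 0.2 cm node enter the rule?** No. It is below the 0.5 cm minimum and inside the 0 to 0.4 cm non-evaluable range. A 25% increase takes it only to 0.2 × 1.25 = 0.25 cm, still below the minimum. Section 6.1.4.2.3 also has a separate rule for nodes under 0.5 cm at baseline: they count as progression on reaching 0.5 cm.

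**Step 3: overlap as printed.** On a 0.1 cm grid from 0.5 to 2.0 cm there are 16 baseline sizes, and all 16 fall in two tiers. The cut-offs for progression (cm) at selected sizes are:

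| Baseline | Tier 1 or 2 | 25% tier |
|---|---|---|
| 0.5 | 0.8 | 0.625 |
| 1.0 | 1.3 | 1.25 |
| 1.1 | 1.5 | 1.375 |
| 1.6 | 2.0 | 2.0 |
| 2.0 | 2.4 | 2.5 |

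The two cut-offs agree only where 1.25b = b + 0.4, that is b = 1.6 cm. Solving 1.25b = b + 0.3 gives b = 1.2 cm, which is outside tier 1. At smaller baselines on the grid the 25% rule calls progression earlier than the absolute rule; from 1.7 cm it calls it later.

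**Step 4: overlap after correction.** With tier 3 starting at 2 cm, one of the 16 sizes still lies in two tiers, namely 2.0 cm, because tier 2 includes its upper bound. Tier 2 gives 2.0 + 0.4 = 2.4 cm, which is +20%. Tier 3 gives 2.0 × 1.25 = 2.5 cm. If meeting either tier is enough, progression starts at 2.4 cm; if both must be met, it starts at 2.5 cm. The text does not say which. At 0.1 cm precision only a 2.0 cm node measured at 2.4 cm is affected.

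**Step 5: with tier 2 ending at 1.9 cm.** A 1.9 cm node progresses at 1.9 + 0.4 = 2.3 cm and a 2.0 cm node at 2.5 cm. No size on the grid is in two tiers, and none is left without a tier.

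**The case against.** The best reply is that the misprint corrects itself. The tiers ascend, a 0.2 cm node cannot be a target node, and the second example starts at 2.5 cm, so a careful radiologist would read 2 cm. On that view the +1150% and the 16-size overlap describe a reading nobody would apply, and what is left is a single 0.1 cm step at one baseline size. Most of this stands, and it is why the severity is low. It does not make the sentence right: the wrong figure appears twice in a rule that determines response status, and the tie at 2.0 cm survives even the charitable reading.

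A reader might also infer a second conflict. Sections 6.0 and 6.2.1.3 apply the endoscopic criterion of 20% or less only to disease that is not radiologically measurable, while Sections 7.0 and 12.0 mention poor clinical response without that limit. The documents do not support calling this a contradiction. Section 7.0 says which patients will have TME after restaging; it does not bar anyone else. Sections 6.0 and 6.2.1.3 are the explicit decision rules. Section 12.0 gives a list of discontinuation reasons that is expressly not exhaustive.

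**Conclusion.** The sentence is wrong as written, in operative text, at low severity. The evidence that 2 cm was meant is strong: the order of the tiers, the arithmetic of the example and the 0.5 cm minimum all point the same way. Read as intended, the remaining defect is one baseline size out of 16 (2.0 cm) and one follow-up size (2.4 cm). It changes a patient's path only if the primary tumor is otherwise responding.

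This assumes that nodes are recorded to 0.1 cm, the precision in which the tiers are expressed. The documents do not give the number of nodes of this size among the 30 planned patients, and it may be zero. It would go too far to infer that the pCR count is biased: any effect on it is unknown and may be nil.

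**What to change.** In Section 6.1.4.2.2:

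- Change 0.2 cm to 2 cm in both places, so that the third tier starts at 2 cm and its first example runs from 2 cm to 2.5 cm.
- Keep the 2.5 to 3.1 cm example as printed. Replacing 3.1 with 3.2 cm would move a cut-off that is not in dispute.
- End the middle tier at 1.9 cm inclusive, so that a 2.0 cm node falls under the 25% tier, as the corrected first example implies.

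Starting the third tier strictly above 2 cm would also remove the tie, but the corrected first example would then no longer belong to its own tier.

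The cost is amendment wording in one subsection. No procedure or data item is added, and the sample size of 30, the stated confidence interval width of 0.36 and the two-stage rule in Section 10.1 are unchanged.

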6.1.4.3 Overall radiologic tumor response status after neoadjuvant LDFRT-FOX

The radiologic response status after neoadjuvant LDFRT-FOLFOX is determined by combining the patient’s status including primary rectal tumor, target lymph nodes, and new disease as defined below:

Primary Rectal Tumor & Target Lymph Nodes	New Sites of Disease	Overall Radiographic Tumor Response Status
CR	No	CR
PR	No	PR
SD	No	SD
Not all evaluated	No	Not evaluated
PD	Yes or No	PD

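### The 25% nodal progression tier is printed as starting at 0.2 cm (almost certainly 2.0 cm), and the PD row of the response table leaves out target-node growth

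*Combined protocol and SAP*

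**What the plan says.** Section 6.1.4.2.2 first fixes which nodes count: "For purpose of restaging, a target lymph node must measure 0.5 cm or more in short axis". It then gives three bands by baseline short axis.

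- 0.5 to 1 cm inclusive: the node "must increase 0.3 cm in size to be considered PD".
- 1.1 to 2 cm: "Nodes between 1.1 and 2 cm short axis inclusive must increase in size 0.4 cm to be considered PD".
- Top band: "Nodes 0.2 cm and greater in short axis must increase in size by 25" percent, with the examples "0.2 cm to 2.5 cm, or 2.5 cm to 3.1 cm".

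The table in 6.1.4.2.3 then defines the response categories. Partial response (PR) needs the product of the primary's two dimensions to fall by at least 20%, no new disease, "And no PD of any target lymph nodes". The PD row has two triggers: a rise of at least 20% in the primary's product, or a new malignant lesion. The second includes "any LN that was normal at baseline (< 0.5 cm short axis) and increased to ≥ 0.5 cm short axis during follow-up". Growth of an existing target node is not listed. Section 6.1.4.3 then builds the overall call from the patient's "status including primary rectal tumor, target lymph nodes, and new disease as defined below".

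Under sections 6.0 and 6.2.1.3, PD on imaging sends the patient to off-protocol chemoradiation followed by total mesorectal excision (TME). So does stable disease (SD) when disease is radiologically measurable.

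**The concern.** These are working thresholds that decide treatment at restaging, and as printed they do not agree with each other.

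The top band starts below the other two, below the 0.5 cm minimum for a target node, and inside the 0 to 0.4 cm range that 6.1.4.1 treats as not evaluable for change. Its first example does not illustrate a 25% rise. The table and the text above it also disagree on whether target-node growth is PD.

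A wrong nodal call matters mainly when the primary has responded, because in measurable disease a patient whose primary has not shrunk by 20% leaves the direct-to-TME path anyway. For a responder, the nodal rule decides between direct TME and chemoradiation first. Diversion also puts non-protocol treatment before the specimen on which pathologic complete response, the primary endpoint, is judged. Section 14.0 does not say how such a patient is counted.

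**Working it through.** **Inputs.** All come from sections 6.1.4.2.2 and 6.1.4.2.3: bands 0.5–1 cm (+0.3 cm), 1.1–2 cm (+0.4 cm) and the top band (+25%, printed from 0.2 cm), plus the two printed examples.

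**Step 1: the printed examples.** Percent change = (after / before − 1) × 100.

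| Growth | Change | Comment |
|---|---|---|
| 0.2 to 2.5 cm (as printed) | 2.5/0.2 − 1 = +1150% | does not illustrate 25% |
| 2.0 to 2.5 cm | 2.5/2.0 − 1 = +25% | exact |
| 2.5 to 3.1 cm (as printed) | 3.1/2.5 − 1 = +24% | 25% needs 2.5 × 1.25 = 3.125 cm |

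With 2.0 cm the first example fits exactly, and the second fits if the threshold is rounded to 0.1 cm.

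**Step 2: conflicts between bands.** Take baseline sizes 0.5, 0.6, …, 2.0 cm (16 sizes) and follow-up sizes in 0.1 cm steps. Count a baseline as conflicting if some follow-up size is PD by the absolute band but not by the 25% tier, or the reverse, where both rules apply.

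| Reading | Conflicting baselines |
|---|---|
| 25% tier from 2.0 cm, +0.4 cm band to 2.0 cm (intended reading) | 1 of 16 |
| 25% tier from 2.0 cm, +0.4 cm band to 1.9 cm (proposed) | 0 of 16 |
| 25% tier from 0.2 cm (literal) | 10 of 16 |

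The single conflict on the intended reading is 2.0 to 2.4 cm: +0.4 cm meets the middle band, but 2.4/2.0 − 1 = +20% does not meet the 25% tier.

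The ten conflicts on the literal reading are:

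- PD by 25% only: 0.5 to 0.7 (+40%), 0.6 to 0.8, 0.7 to 0.9, 0.8 to 1.0, 1.1 to 1.4 and 1.2 to 1.5 cm.
- PD by +0.4 cm only: 1.7 to 2.1, 1.8 to 2.2, 1.9 to 2.3 (+21%) and 2.0 to 2.4 cm.

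**Step 3: text against table.** Take a primary whose product is down by at least 20%, and a target node that grows from 1.5 to 1.9 cm (+0.4 cm).

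- By 6.1.4.2.2 the node is PD.
- In the 6.1.4.2.3 table, CR fails because the node is not below 0.5 cm, and PR fails because it bars nodal PD.
- The PD row is not met: there is no new lesion and no growth of the primary. The patient falls to SD by default.
- Section 6.1.4.3 combines primary and target nodes, and 6.0 acts on PD found by imaging. Read together with 6.1.4.2.2, they give PD.

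**Step 4: effect on treatment.**

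- *Overlap at 2.0 cm.* Take a responding primary and a node going from 2.0 to 2.4 cm. The +0.4 cm band sends the patient to chemoradiation; the 25% tier leaves PR and direct TME.
- *Table gap.* In measurable disease SD and PD both leave, so only the recorded category changes. Outside measurable disease there is a narrow exception. Suppose the primary is not measurable, endoscopic response exceeds 20%, and the only target node is 0.5–0.9 cm and grows 0.3 cm. SD then allows direct TME, and PD does not.

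**The case against.** The strongest reply is that the protocol corrects itself. The 0.5 cm minimum, the ascending bands and the second example all point to 2.0 cm, and a radiologist will probably read it so. The 10 of 16 then describes a reading nobody should use. That is fair, and the count is given here only as the literal bound.

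It can also be said that the remaining overlap is a single size, and that the corrected example (2.0 to 2.5 cm) places a 2.0 cm node in the 25% tier. That helps, but the middle band still expressly includes 2 cm, so the conflict stays on the page.

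On the table, the PR row makes sense only by importing the nodal rule from the text, and 6.1.4.3 covers target nodes. This too is right: the rule exists, and the fault is a mismatch between text and table. A row that lists the triggers for PD should still list all of them.

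Last, internal iliac nodes follow the absolute-increase rules. If that means the absolute bands alone, ending the middle band at 1.9 cm leaves a 2.0 cm iliac node without a rule. On that reading, however, iliac nodes above 2 cm already have none, so the clause needs clarifying whichever boundary is chosen.

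**Conclusion.** The concern holds and is minor. The 0.2 cm bound is wrong as written. On the intended 2.0 cm reading, one conflict remains among the 16 baseline sizes (2.0 to 2.4 cm), and the PD row omits a trigger that the text defines.

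This rests on 2.0 cm being the intended value, which the text supports strongly, and on measurement in 0.1 cm steps. The counts are size steps, not patient frequencies. The documents give no distribution of node sizes, so the number of patients affected cannot be computed.

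The consequence is modest. A wrongly diverted patient receives chemoradiation, which section 1.3 describes as the current standard of care, and then TME. No sample size, alpha or power figure is affected.

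**What to change.** One short amendment, with no new scans, readers or patients:

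1. In 6.1.4.2.2, change 0.2 cm to 2.0 cm in both places and end the +0.4 cm band at 1.9 cm. State whether the 25% threshold is rounded to 0.1 cm, and whether the 25% tier applies to internal iliac nodes.
2. In the PD row of 6.1.4.2.3, add PD of any target lymph node under 6.1.4.2.2.
3. Ask the radiology lead whether a node going from 0.4 to 0.5 cm should count as a new malignant lesion, given that 6.1.4.1 treats nodes of 0–0.4 cm as not evaluable for change. This is a query; no rule is proposed.
4. As housekeeping, reconcile the nodal cut-off for complete response: below 0.5 cm in the table, 1.9 cm or less in 6.1.4.2.2. This changes no treatment between CR and PR, since both go directly to TME.
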